2.0 Rationale and Specific Aims

We hypothesize that patients with T1DM who have reduced pancreatic volume will have improved glycemic responsiveness, reduced hypoglycemia, and improved symptoms of pancreatic exocrine insufficiency (PEI) when treated with pancreatic enzyme replacement. To test our hypotheses, we will employ a double-blinded crossover study. This study will be a pilot study to gather preliminary information on potential effect size in preparation for a larger study if supported by these results. The study will enroll approximately 15 adult subjects with T1D who will receive both pancreatic enzyme replacement (Creon) or placebo each for 7 days in a random order. The effect of the intervention will be monitored by continuous glucose monitoring, diet recording, capsule counts, a mixed-meal tolerance test, and a survey to assess symptoms of PEI. This study design will allow for estimation of the effect of pancreatic enzyme replacement on the measured parameters.

Aim 1 will provide preliminary estimates of the effect of enzyme replacement on glucose responsiveness, variability, and hypoglycemia. We will download and analyze CGM data to determine changes occurring in measures of glycemic variability and in the duration and severity of hypoglycemia. Data will be divided into 4 7-day blocks including a run-in period, treatment A, a wash out period, and treatment B. Participants will track their meal composition, report daily exercise duration, and a capsule count will be obtained. At the end of treatment A and treatment B, participants will undergo a mixed meal tolerance test (MMTT) in which glucose, C-peptide, GLP-1, GIP, and glucagon will be measured at defined timepoints.

Aim 2 will provide an initial assessment of the effect of enzyme replacement on symptoms of pancreatic exocrine insufficiency in T1D. We will use the PEI-Q to quantitate symptoms of PEI and their relative change during enzyme replacement at each of the 4 intervals. The frequency and degree of PEI symptoms has not been objectively measured in T1D patients previously.

We will obtain information on the adherence to the intervention and will obtain initial information on median and standard deviation for measured variables that will inform future studies. We will perform a paired t-test to provide an initial assessment of outcomes between groups.

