5.1.2 Initial Contact with Potential Participants

Participants will be contacted by telephone. The initial discussion will provide information about the study and assess whether the subject might be eligible to participate in the study. Study personnel will ask the potential subject to confirm his or her:

- Diagnosis of T1DM
- Age
- Weight
- Height
- Diabetes duration
- Medications
- Food preferences and restrictions
- Use of CGM
- Ability to read and speak English

Inclusion and exclusion criteria are listed in table 1. We will invite eligible subjects to participate in the initial screening visit. The initial screening visit will occur at Vanderbilt University Medical Center. The participant will receive an electronic or paper copy of the informed consent document to review prior to the initial screening visit.

5.2 Enrollment

A member of the study team (i.e. key study personnel, KSP) will obtain written, informed consent at the beginning of the screening visit as detailed in section 6.1.1.1. Once consent is obtained, the participant will be enrolled in the study.

5.3 Randomization

Patients will be randomized for order to receive pancreas enzyme replacement or placebo. The Vanderbilt Investigational Drug Services (IDS) pharmacy will do the randomization. They will dispense the randomized capsule bottles for weeks A and B to the study team to be given to the study participants.

5.4 Participant Compensation Participants will receive \$200 for each completed MMTT for a total of up to \$600 for participation in the study.

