10.0 Statistical Considerations

10.1 Recruitment

We have targeted an accrual of 15 participants in this pilot study. We will estimate the effect size and variance of the intervention on glycemic variability and symptoms. We will also ascertain the intra-individual variation from comparison between our two non-treatment intervals (run-in and wash-out periods) which will set a lower bound on measurable effects. To estimate the pilot study's optimum accrual, we utilized the method of Whitehead et al. which proposes stepped increases in sample size based on the anticipated standard difference, d, between interventions^{1,2}. We defined the minimum important difference (MID) in low blood glucose index, a measure of low blood glucose from CGM data) between enzyme replacement and placebo interventions as 1 (difference in values of 3 for more variable and 2 for less variable as reflected in clinical experience) and estimated a pooled SD of 1.29 based on our review of CGM data from other studies. If d=MID/SDpooled=1/1.29=0.77, a sample size of 15 participants per arm will optimize future sample size calculations for a definitive study.

10.2 Statistical Analysis Statistical analysis will be performed using a paired samples t-test to compare differences between the two groups.

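### Treatment order is randomised, but no named treatment comparison accounts for period, so any change between the two treatment weeks is counted as error

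*Protocol*

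**What the plan says.** **Design.** Protocol 5.3 states: "Patients will be randomized for order to receive pancreas enzyme replacement or placebo". Protocol 6.1.1.6 plans equal numbers in the two orders. Aim 1 in Protocol 2.0 sets the timeline: "Data will be divided into 4 7-day blocks including a run-in period, treatment A, a wash out period, and treatment B".

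**Named tests.**
- Protocol 2.0: "We will perform a paired t-test to provide an initial assessment of outcomes between groups".
- Protocol 10.2: "Statistical analysis will be performed using a paired samples t-test to compare differences between the two groups".
- SAP, Primary Outcome Analysis: a Wilcoxon matched-pairs test for C-peptide AUC and a t-test, in a matched analysis, for the PEI-Q severity score.

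None of these includes a period or sequence term. The SAP's Secondary Objectives list CGM, hormone and diet analyses without naming a test, so Protocol 10.2 is read here as covering the CGM measures.

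**Use of the results.** Protocol 10.1 states: "We will estimate the effect size and variance of the intervention on glycemic variability and symptoms". Protocol 2.0 also promises "initial information on median and standard deviation for measured variables that will inform future studies".

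**Analysis set.** The SAP analyses only participants who complete both treatments, and allows exclusion for poor agreement between capsule count and diet history.

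**The concern.** Below, week A is the first treatment week and week B the second. Outcomes may move between them for reasons unrelated to treatment. The documents describe possible routes: diet logging throughout, repeated questionnaires and meal tests, and continued insulin adjustment by outside endocrinologists.

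In participants who take Creon second, such a shift adds to the Creon-minus-placebo difference. In those who take it first, it subtracts. The two orders then centre on different values, and a test that pools all the differences reads that separation as person-to-person noise. The design already supplies the two groups needed to remove it.

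Two things are at stake. The first is the width of the pilot's own intervals. The second is the SD of within-person differences, if a later crossover is planned from it. Bias is a lesser matter and grows only if the completers are unevenly split between the orders.

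**Working it through.** **The plan's own figure.** Protocol 10.1 takes a difference of 1 in low blood glucose index and "estimated a pooled SD of 1.29 based on our review of CGM data from other studies". Then 1/1.29 = 0.775, given as 0.77. The step from there to 15 uses a rule the documents do not reproduce, so it cannot be rechecked, and nothing below depends on it. Fifteen cannot split equally; 8/7 is the closest.

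**Model.** For participant i, the Creon-minus-placebo difference is

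D_i = τ + s_i·π + e_i, with s_i = +1 if Creon is in week B and −1 if in week A.

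Here τ is the treatment effect and π the week-A-to-week-B shift. The e_i are normal with SD 1, so π is in units of SD_d, the within-order SD of the differences. The documents give no value for π; 0.25, 0.5 and 1.0 are assumptions.

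**Variance and bias of the unadjusted analysis.**
- E[var(D)] = 1 + π²·4·n1·n2/(n(n−1)). At 8/7 the coefficient is 4·8·7/(15·14) = 1.067.
- Bias = π·(n1−n2)/n. At 8/7 this is π/15; at an assumed 8/4 it is π/3.

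**Interval width and type I error at 8/7** (simulation, 200,000 runs per setting; half-widths are means for 95% t intervals, in SD_d):

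| π | Variance factor | Paired t half-width | Period-adjusted half-width | Ratio | Paired t type I error |
|---|---|---|---|---|---|
| 0 | 1.00 | 0.544 | 0.548 | 0.99 | 5.0% |
| 0.25 | 1.07 | 0.562 | 0.548 | 1.02 | 4.4% |
| 0.5 | 1.27 | 0.613 | 0.548 | 1.12 | 3.1% |
| 1.0 | 2.07 | 0.786 | 0.548 | 1.43 | 0.8% |

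The adjusted analysis keeps type I error at about 5% and the pooled within-order variance at 1.00 throughout. The two intervals are equally wide at π of about 0.13 for 8/7, 0.27 for an assumed 8/5 and 0.39 for an assumed 8/4. At 8/4, bias offsets the conservatism: paired-t type I error is 5.2%, 5.6% and about 5% at the three shifts.

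**Consequence for planning.** Take a future crossover with difference 1, SD 1.29 per treatment, two-sided 5% and 90% power (the power is assumed). With within-person correlation ρ (assumed), SD_d = 1.29·√(2(1−ρ)), and its square is multiplied by 1 + 1.067π². Noncentral t gives:

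| ρ | No shift | 0.25 | 0.5 | 1.0 |
|---|---|---|---|---|
| 0.3 | 27 | 29 | 33 | 53 |
| 0.5 | 20 | 21 | 25 | 39 |
| 0.8 | 10 | 10 | 11 | 17 |

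Per-treatment variances rise by π²·n1·n2/(n(n−1))·2(1−ρ). At ρ = 0.5 and 8/7 that is 1.7%, 6.7% and 27%. The choice of test does not alter these.

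**Would the planned drift check catch it?** Protocol 10.1 says: "We will also ascertain the intra-individual variation from comparison between our two non-treatment intervals (run-in and wash-out periods". Those weeks are two weeks apart, as are weeks A and B. With 15 people and the same SD_d assumed, the 95% half-width is t(0.975, 14)/√15 = 2.145/3.873 = 0.55 SD_d, so it could not rule out a shift of 0.5.

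**Rank tests.** In 30,000 simulated runs with normal data at 8/7, Wilcoxon signed-rank half-widths were 0.561, 0.578, 0.634 and 0.832 at π = 0, 0.25, 0.5 and 1.0. The halved rank-sum interval stayed at about 0.596. It is narrower only above roughly 0.34–0.35 SD_d. The exact levels differ slightly (95.2% against 96.0%), so this threshold is approximate.

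**The case against.** The strongest reply is that little may be lost. Equal orders are planned, so the paired estimate is nearly unbiased and the test errs on the safe side. The participants have had diabetes for at least a year and keep their usual diet and care. In index units, with ρ = 0.5, shifts of 0.25, 0.5 and 1.0 SD_d are 0.32, 0.65 and 1.29. The largest therefore exceeds the difference of 1 that the protocol treats as important, and nothing in the documents suggests drift of that size. At 0.25 the cost is a 2% wider interval and one more planned participant. Sampling error is far larger: with 14 degrees of freedom the 95% limits for a variance are 0.54 to 2.49 times the estimate, which alone moves the planned 20 to between 12 and 46. The protocol speaks of SDs per variable and a pooled SD, and planning from those does not depend on the test.

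All of this stands as a limit on the size of the problem. It does not remove the problem, because the shift is avoidable error in an estimate the pilot exists to provide, and avoiding it costs almost nothing.

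The other data collected do not fill the gap. The run-in and wash-out weeks give CGM data and, under Aim 2 of Protocol 2.0, PEI-Q at all four intervals (Protocol 6.1.4.4 lists only three time points). There is a baseline meal test but none in the wash-out. None of these adjusts the treatment comparison.

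It is also fair that applying Protocol 10.2 to CGM is an inference, and that a linear model for C-peptide AUC gives up the SAP's rank approach. The fix therefore allows the Wilcoxon test to stay.

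**Conclusion.** The concern holds. Every treatment comparison with a named test omits period, and nothing else in the documents adjusts for it. At 8/7 the consequence is lost precision and a conservative test: negligible below about 0.13 SD_d, 2% in interval width at 0.25 and 12% at 0.5. The 43% at 1.0 is best read as an extreme. Bias becomes worth noting only if completers-only analysis or adherence exclusions unbalance the orders.

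The inflated planning variance matters only if a later crossover is planned from the SD of within-person differences. The shifts, correlations, power and uneven splits are all assumptions. The omission does not invalidate the trial's result, and correcting it is a cheap improvement that should be made.

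**What to change.** Change Protocol 10.2 and the SAP's Primary Outcome Analysis as follows.

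- **Outcomes compared by t-test (PEI-Q, and CGM measures under Protocol 10.2).** Fit a model with treatment, period and participant. For completers this equals an unpaired t-test of the week-A-minus-week-B differences between the two orders, with the estimate and interval halved.
- **Reporting.** Give the within-order SD of the differences, for future planning, and the number of completers in each order.
- **C-peptide AUC.** Either use the same model, or keep the Wilcoxon test and add the period-adjusted result as a sensitivity analysis. The second leaves the SAP's primary test unchanged. Do not simply substitute the halved rank-sum test, which widens the interval unless the shift is above roughly 0.34–0.35 SD_d.

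The cost is wording and one degree of freedom. If there is no shift, the adjusted t interval is about 1% wider at 8/7 (0.548 against 0.544), 4% at an assumed 8/5 (0.613 against 0.592) and 7% at an assumed 8/4 (0.665 against 0.621). The completer version is an ordinary unpaired t-test, so the software named in the SAP suffices.

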11.0 Privacy/Confidentiality Issues

A database will be designed for this study using REDCap (Research Electronic Data Capture) tools. REDCap is a secure, web-based application designed to support data capture for research studies, providing validated data entry, audit trails, seamless data downloads to common statistical packages, and mechanisms for importing data from external sources. It will reside on a secure server with access provided exclusively to the research personnel. Subjects will be identified with a study identification number. A key to the subject identification number will be kept in a separate locked file drawer to which only the Principal Investigator and research coordinators have access. Reports will thereby be generated without Protected Health Information (PHI) data, and access will be restricted so that statisticians, etc. don't have access to all data.

Risk of leakage of PHI is minimized by keeping paper records in a locked cabinet and maintaining computerized records in the password protected REDCap data base. The principal investigator and the research staff are trained in HIPAA privacy regulations. The participant's identification is concealed, and a number is used as the identifier instead of the subject's name. Only the principal investigator or members of the research team will have the list of study patient's names as the correlate with the study number.

Pancreatic enzyme replacement and glucose regulation in Type 1 diabetes

NCT05266963

Statistical Analysis Plan

12/4/2023

Statistical Analysis Plan

NCT05266963 - Pancreatic Enzyme Replacement and Glucose Regulation in Type 1 Diabetes (CREON)

Background

In T1D, there is significant reduction in pancreas volume. The biological impact of this is not known. Because islet cells make up a small fraction of pancreas size, the major reduction in volume is due to loss of exocrine tissue. Since patient with T1D have substantial loss of exocrine tissue and pancreatic enzymes support glucoe regulation and pancreas function, this study tests the hypothesis that pancreatic enzyme replacement will improve C-peptide secretion to regulate glucose excursions and/or will improve symptoms of pancreatic enzorine insufficiency. This document provides additional description of the analysis plan and complements the protocol document where study details are provided.

Primary objective

Aim 1: To assess impact of pancreas enzyme replacement on C-peptide auc in subjects with T1D and reduced pancreas volume

Aim 2: To assess the impact of pancreas enzyme replacement on symptoms of pancreatic exocrine insufficiency (PEI) in T1D.

Secondary Objectives

Secondary assessments will be made to explore mechanisms of effect if the primary outcome is met. These could include analysis of CGM data, measure of circulating hormones and cytokines, assessment of dietary intake.

Trial Design

The study is a single center, double-blinded randomized cross over design in which subjects receive Creon or placebo each for 1 week with a 1 week washout period between.

Eligibility

Inclusion Criteria	Exclusion Criteria
 Diagnosed with T1DM for at least	 History of celiac disease or
12 months Age over 18 Total daily dose of insulin greater	inflammatory bowel disease Unwilling to temporarily discontinue
than 0.6u/kg/day	use of medication or supplements

 Current use of a CGM 	other than insulin to control blood
 Current use of smart phone 	glucose
 Able to read and speak English 	 Pregnant or breast feeding
 Willingness and ability to download and provide CGM and pump (if applicable) data Reduction of pancreas volume (<0.6mL/kg BW) 	 Following a restrictive diet (such as very low carb diet) History of major bowel or bariatric surgery

Treatment

Participants will continue their standard care for diabetes with calculation and adjustment of doses per their primary endocrinologists.

Participants will receive a range of 50,000-100,000 lipase units per meal (approx. 2 Creon 36,000 capsules) and 25,000-50,000 per snack (1 capsule). The participant will be instructed to take same number of capsules of placebo. Participant and provider will be blinded to capsule assignment.

Assessment of Outcomes

Outcomes will be assessed at baseline and at completion of each treatment week.

Hypothesis

The null hypothesis to be tested is that there will be no difference between the treatment groups.

Blinding

Subjects and investigators will be blinded to treatment assignment. Blinded drug or placebo is provided by the VUMC Investigational Pharmacy.

Analysis

Only subjects completing both arms will be included in the final analysis.

Data collection

Demographics: Participants age, sex, weight will be obtained.

Diabetes Management: Participants estimated or actual insulin dosing, CGM download, diet history, pancreas volume index will be obtained.

Study results: Participants will complete MMTT and PEI questionnaires.

Adherence

Pill counts will be obtained. Participants with significant discrepancy between pill count and diet history may be excluded from analysis.

Primary Outcome Analysis

C-peptide AUC will be calculated from MMTT data. Data from creon and placebo intervals will be compared for each individual in a matched analysis. Comparison will be made by Wilcoxon matched-pairs assessment.

Severity score will be calculated from the PEI-Q survey. Data from creon and placebo intervals will be compared for each individual in a matched analysis. Comparison will be made by t-test

Statistical Software

Analysis will be performed on Prism Ver 10 or on current version of Microsoft excel.

Exploratory Analysis

Additional analyses may be performed if primary endpoint is met to provide mechanistic insight or if requested by journal or editorial review.

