Our group has developed advanced, standardized approaches to image the pancreas and has applied this approach to understanding the role of whole pancreas pathology in T1D, a disease traditionally thought to only involve the pancreatic islet. An example image of the pancreas of a control participant and participant with recent-onset T1D is shown in Figures 1B and 1C, respectively, with the pancreas outlined in white. Within 100 days of diabetes onset, individuals with T1D (n = 51) had a smaller pancreas (median volume = 29.6 ml) than controls (n = 58, median volume = 47.8 ml, p < 0.001), including when normalized by individual weight (p<0.001). In multiple autoantibody-positive individuals, the pancreas volume was significantly larger than the T1D cohort (p=0.014), but smaller than the control cohort (p=0.019). To account for normal adolescent growth, we compared pancreas volume and weight in control study participants. In the control cohort, pancreas volume correlated with participant weight (Figure 1D, R = 0.76, p < 0.001). Thus, to account for changes in pancreatic volume during normal adolescent growth, pancreas volume was normalized by participant weight yielding what has been termed the pancreas volume index. Normalization by body surface area and BMI were also explored but were inferior to normalizing by weight. At the first study time point, the pancreas volume index was smaller in participants with recent-onset T1D than controls (Figure 1E; median 0.931ml/kg in controls and 0.615 ml/kg in T1D, p < 0.001). Pancreas volume index was smaller in participants with T1D when adjusted for age, sex, and BMI (mean difference -0.279 ml/kg with 95% CI -0.352 to -0.205, p < 0.001 from linear regression). Key data from these early studies are highlighted in Figure 1 and in our published work. As highlighted in Figure 1, pancreas volume declines over the first year after diagnosis (Figure 1F, G). This finding demonstrates the small

Protocol Version #: 6 Protocol Date: 04DEC2023 pancreas in T1D and the presence of an underlying process resulting in ongoing changes in the pancreas after diagnosis with T1D; the physiologic consequences of these changes are not known.

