6.1.1.6 Randomization and Treatment Plan

Participants will be randomized for order in which enzyme replacement or placebo is received. An equal number of participants will receive either order (A/B or B/A). Participants will receive a range of 50,000-100,000 lipase units per meal (approx. 2 Creon 36,000 capsules) and 25,000-50,000 per snack (1 capsule). The participant will be instructed to take same number of capsules of placebo. Participant and provider will be blinded to capsule assignment.

- 6.1.2 Study visit (baseline)
 - 6.1.2.1 Demographic and history information will be obtained.
 - 6.1.2.2 Participant will be counseled on using and uploading devices and information.
 - 6.1.2.3 Participant will complete a baseline Mixed Meal Tolerance Test (MMTT). The test will be administered according to the well established practices used in the TrialNet clinical T1D research program and described in the included appendix. This baseline visit will take place in the Adult Clinical Research Center (CRC).
- 6.1.3 Study Visit (end of week A)
 - 6.1.3.1 On last day of week A, subject will have an MMTT at the Adult CRC.

6.1.4 Study Visit (end of week B/end of study) This visit will include an MMTT at the Adult CRC and will be scheduled on the last day of week B.

6.1.4.1 History and measurements

Protocol Version #: 6 Protocol Date: 04DEC2023 The PI or designee will review each subject's clinical history and take anthropometric measurements.

6.1.4.2 Continuous glucose monitor and insulin pump data collection

Continuous glucose monitor and insulin pump will be downloaded into a HIPAA and FDAcompliant cloud-based, data-integration platform such as Dexcom Clarity, Medtronic Carelink, or Tidepool.

Information that will be collected from the continuous glucose monitor download will include (but not be limited to):

- Percent of time spent above the glycemic target of 140 mg/dL
- Percent of time spent in the glycemic target of 70 140 mg/dL
- Percent of time spent below the glycemic target of 70 mg/dL
- Percent of time spent in hypoglycemia below 50 mg/dL
- Average blood glucose
- Blood glucose standard variation
- All blood glucose values during the study interval

Information that will be collected from the insulin pump download will include (but not be limited to):

- Average total daily dose of insulin
- Average bolus amount of insulin per day
- Average basal amount of insulin per day

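### The same-dated protocol and SAP give Aim 1 different outcomes (CGM glucose measures versus MMTT C-peptide AUC), and neither says which prevails

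*SAP*

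**What the plan says.** Protocol 2.0 sets out the first aim as follows: "Aim 1 will provide preliminary estimates of the effect of enzyme replacement on glucose responsiveness, variability, and hypoglycemia". The data source is CGM: "We will download and analyze CGM data to determine changes occurring in measures of glycemic variability and in the duration and severity of hypoglycemia". The same paragraph adds a mixed meal tolerance test (MMTT) "in which glucose, C-peptide, GLP-1, GIP, and glucagon will be measured at defined timepoints". C-peptide is thus measured under the protocol's Aim 1, but as one analyte of five, with no AUC and no priority. The protocol names no primary outcome. Section 10.1 takes its only effect size from a CGM measure: "We defined the minimum important difference (MID) in low blood glucose index". Section 10.2 specifies a paired t-test without naming an outcome.

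The SAP, under Primary objective, says "Aim 1: To assess impact of pancreas enzyme replacement on C-peptide auc in subjects with T1D and reduced pancreas volume". Its Primary Outcome Analysis compares C-peptide AUC between the Creon and placebo intervals by the Wilcoxon matched-pairs test. Under Secondary Objectives, CGM analysis is one of several assessments that could be made, and only on condition that the primary outcome is met. LBGI does not appear in the SAP.

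The protocol carries the line "Protocol Version #: 6 Protocol Date: 04DEC2023". The SAP is dated 12/4/2023, which is the same day if read month first. The SAP's Background says that it complements the protocol. Neither document states an order of precedence.

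**The concern.** Two documents of the same date use one label for two different questions. The later-document rule cannot settle it, and the SAP's account of itself as a complement implies that the protocol's aim still stands.

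Two things are at stake.

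- **Reporting.** An analyst who follows the SAP to the letter, and finds no C-peptide effect, need not analyse CGM at all. The glucose estimates that the protocol gives as the purpose of Aim 1 would then go unreported, including LBGI, the only outcome with a stated minimum important difference. The study is meant to supply effect sizes "in preparation for a larger study if supported by these results", so these estimates are a main product of the pilot.
- **Selection.** With no precedence rule, a report could present either C-peptide AUC or a CGM measure as the Aim 1 result, and cite a current document in support of each.

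**Working it through.** **Side by side**

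| Item | Protocol v6 | SAP |
|--|--|--|
| Date | 04DEC2023 | 12/4/2023 |
| Aim 1 outcome | Glucose responsiveness, variability, hypoglycaemia (2.0) | C-peptide AUC (Primary objective) |
| Place of C-peptide | One of five MMTT analytes (2.0) | Primary |
| Place of CGM | Main data source for Aim 1 (2.0) | Optional, conditional secondary |
| LBGI | Basis of the sizing (10.1) | Not mentioned |
| Test | Paired t-test (10.2) | Wilcoxon matched-pairs for C-peptide AUC |
| Precedence | Not stated | Not stated; complements the protocol |

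The rows for outcome, CGM, LBGI and test cannot all be followed at once.

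**The plan's own figure.** Protocol 10.1 takes a minimum important difference of 1 and a pooled SD of 1.29. Then d = 1/1.29 = 0.775; the protocol prints 0.77. The step from d to 15 per arm uses a cited stepped rule whose table is not in the documents, so it cannot be reproduced here. The point does not depend on it. What matters is that both inputs belong to LBGI.

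**Effect of a free choice between two outcomes.** Neither document states alpha or sidedness, so two-sided 5% is an assumption. The other assumptions are 15 complete pairs, no treatment effect on either outcome, and normal paired differences.

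- One named contrast: false-positive chance 5%.
- Two independent contrasts, either of which may be presented: 1 − (1 − 0.05)² = 1 − 0.9025 = 9.75%.
- Correlated contrasts, by simulation:

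| Correlation between the two paired differences | 0 | 0.5 | 0.8 |
|--|--|--|--|
| Paired t-test on both (40,000 trials) | 9.9% | 9.1% | 7.9% |
| Paired t-test on the CGM measure, Wilcoxon on C-peptide AUC (20,000 trials) | 9.5% | 8.9% | 7.6% |

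Both sets of tests give about 8% to 10%. The correlation between LBGI and C-peptide AUC is not in the documents, hence the range.

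**The case against.** The strongest reply is that the SAP is the analysis document and is clear. It places C-peptide AUC under the primary objective, gives the matched comparison and the test, and ranks CGM below it. The protocol's Aim 1 is pilot estimation with no success criterion; the idea of an outcome being met occurs only in the SAP. The outcome sets also overlap: the protocol measures C-peptide under Aim 1, and the SAP's hypothesis ties C-peptide secretion to glucose excursions. LBGI is named for sizing, never as the Aim 1 test.

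All of that stands, and it rules out several stronger readings that a reader might infer:

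- **That no contrast decides Aim 1 anywhere.** The SAP alone fixes one. The gap lies between the documents.
- **That one result could pass under one document and fail under the other.** The protocol sets no criterion that could be failed.
- **That eight contrasts compete for Aim 1.** Adding the six CGM summaries in Protocol 6.1.4.2, such as "Percent of time spent below the glycemic target of 70 mg/dL", to C-peptide AUC and LBGI gives eight, and a simulated chance of at least one significant result of about 26% at a common correlation of 0.5. But 6.1.4.2 is a list of data to be collected, and neither document makes its items Aim 1 tests. Three of them (time above, within and below 70–140 mg/dL) sum to 100%, so their paired differences sum to zero and cannot share a common correlation of zero or more.
- **That a rate of disagreement between the two outcomes measures the harm.** Such a rate needs an assumed effect or power for each outcome, which the documents do not give. Any two imperfectly correlated outcomes will sometimes differ in significance, even under a sound hierarchy.
- **That the choice is being held until after unblinding, or alone decides the larger study.** The documents do not say the first. The larger study depends on the results overall, which include Aim 2 symptoms.

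The reply does not remove the mismatch. A SAP that complements a same-dated protocol does not replace that protocol's aim, and its condition on CGM analysis allows the aim to go unanswered.

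**Conclusion.** The concern holds in this form: the current protocol and SAP do not agree on the Aim 1 outcome or its test, and nothing says which prevails. The certain consequence is structural. Following the SAP as written can leave the protocol's Aim 1 estimates, and the outcome behind its sizing, unreported. The inflation is illustrative: about 8% to 10% instead of 5%, if either C-peptide AUC or LBGI could be presented as the Aim 1 result. It rests on an assumed two-sided 5% level, 15 pairs, no effect, and a correlation between 0.8 and 0. For a pilot this should be corrected, but it does not invalidate the design.

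**What to change.** Before unblinding:

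1. Name the same Aim 1 outcome in Protocol 2.0 and 10.2 and in the SAP. The smallest change to the SAP keeps C-peptide AUC as primary and names LBGI as the lead CGM secondary outcome. If the sponsor prefers the glucose aim, name LBGI as primary and relabel C-peptide AUC as mechanistic.
2. State one test for the deciding contrast in both documents, replacing the present split between paired t-test and Wilcoxon.
3. Delete the SAP's condition that ties CGM analysis to success of the primary outcome. Report the Creon–placebo differences in LBGI and the other CGM measures with 95% confidence intervals whatever the primary shows. Label those that are not the deciding outcome secondary or exploratory.
4. In Protocol 10.1, say that the minimum important difference and SD refer to LBGI, and give its status. State which document prevails if they differ.

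The cost is a few sentences in each document. CGM data are already to be collected under both, so no new visits, data or participants are needed. The downside for the sponsor is that a favourable result on a non-deciding outcome can no longer be presented as meeting Aim 1.
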